9.7.3 Secondary analyses

9.7.3.1 Patient age, indication and prescriber specialty

The following analyses will be performed:

- Patient age (mean age, by age groups, 13-20 years, 21-35 years, 36-49 years)
- Indication (diagnosis related to the oral retinoid prescription at the day of oral retinoid prescription or in the last 12 months before oral retinoid initiation)
- Prescriber specialty (Germany, Spain, and Sweden; not available for France)

9.7.3.2 Exposure

The following variables of exposure will be analysed:

Prescription length

The length of prescription will be determined by the date of prescription (or prescription fill/dispensing) plus the expected number of days of supply based on the days' supply reported with this prescription or, when not available, pack size and the recommended daily dose by the physician (if available) or, by default, according to the information of strength connected with the prescription and SmPC. The length will be provided in days.

The following analyses will be performed:

- Average length of prescriptions per treatment episode
- Overall number of prescriptions per patient

Duration of treatment

The duration of treatment will be analysed through the recorded prescriptions in the databases. The date of the first prescription issued (or filled) will be considered as treatment start date. End of treatment duration will be defined by the date of the last prescription plus the number of days' supply of this last prescription. Consecutive prescriptions of oral retinoids will be considered as one treatment episode (allowed gaps between prescriptions will be provided in the statistical analysis plan). The duration of treatment episodes will be provided in days.

The following analyses will be performed:

- Duration of treatment episodes
- Number of prescriptions per treatment episode
- Number of treatment episodes per patient

Average daily dose

The average daily dose will be analysed over a treatment episode based on dosage strength, pack size or day supply and number of prescriptions per episode.

9.7.3.3 *Pregnancy and pregnancy outcomes*

The following analyses will be performed for the pre-implementation and the post-implementation periods:

- Number of pregnancies exposed to oral retinoids
- Incidence rate of pregnancies exposed to oral retinoids
- Information on pregnancy outcome (i.e., live births, termination, stillbirth, miscarriage, or recorded birth defect) will be provided when available in the databases

If the information on trimester, start date of pregnancy, or delivery/end of pregnancy date is available, the pregnancy will be considered exposed if at least one oral retinoid prescription was recorded in the period between the assumed dates of pregnancy start and delivery/end of pregnancy. In case information on pregnancy trimester or start date or delivery/end of pregnancy date is not available in the data source, a pregnancy will be considered as exposed to oral retinoids if at least one oral retinoid prescription was issued within 90 days before or within 180 days after the first record of a given pregnancy.

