To evaluate the changes in the prescribing and monitoring practices following the update of the PPP in females of childbearing potential receiving prescriptions of the oral retinoids acitretin, alitretinoin, or isotretinoin by comparing the following key elements of the PPP between the pre- and the post-implementation period:

- Contraceptives* before, during, and after treatment with oral retinoids
- Time interval between prescription dates for oral retinoids during treatment episode
- Laboratory pregnancy tests – where available - before, during, and after treatment with oral retinoids

* contraceptive methods that require prescription and which are, therefore, captured in the administrative databases

Secondary objectives:

- To describe the patient profile during the pre-and the post-implementation period, with respect to:
 - Patient age
 - Indication for oral retinoids
- To describe the prescriber specialty during the pre-and the post-implementation period
- To describe the exposure characteristics during the pre-and the post-implementation period, with respect to:
 - Active substance
 - Dose
 - Treatment duration
- To describe the incidence of pregnancies exposed to oral retinoids during the pre- and the post-implementation period
- To stratify the key elements of the PPP described in the primary objective by oral retinoid substance
- To describe trends in the physician's prescribing and monitoring practice of oral retinoids with respect to measures of the PPP (contraceptive use and performance of pregnancy tests) over the entire duration the study

Study design:

This is a multicountry, multisource, observational cohort study in females of childbearing potential receiving oral retinoids (i.e., acitretin, alitretinoin and isotretinoin) using a pre-post design. This study will cover time periods before and after the implementation of the updated RMMs related to the PPP update. The study will be based on secondary use of data extracted from established longitudinal healthcare databases (claims, primary care database, national registries). The pre-implementation period consists of 2 distinct phases, a 2-year phase (07/2014 to 06/2016) prior to the start of the referral in July 2016 and a 2.5-year phase between the start of the referral and the distribution of EM for the updated PPP in Q4 2018. The post-implementation period captures the 2-year phase after the distribution of the EM (01/2019 to 12/2020).

Population:

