9. RESEARCH METHODS

9.1 Study Design

This is a multicounty, multisource, observational cohort study in females of childbearing potential receiving oral retinoids (i.e., acitretin, alitretinoin and isotretinoin) using established data sources in different European countries (i.e., France, Germany, Spain, and Sweden)

The study will employ a pre-post design to evaluate the effectiveness of the implementation of the updated RMMs with respect to the PPP according to the following schedule:

- Pre-implementation period: period prior to the date of the implementation of the updated RMMs
- Post-implementation period: period after the implementation of the updated RMMs

Periods will be defined as (also see Figure 1):

Pre-implementation period: The period before the implementation of the updated RMMs. The RMM tools will be distributed in the fourth quarter 2018 (the exact date may vary depending on the country). The pre-implementation period captures two periods:

- Pre-referral: the 2-year period before referral start in July 2016. This period will be used for the before and after comparison with the post-implementation period.
- Post-referral: the 2.5-year period between the referral start date in July 2016 and the distribution of the RMM tools in the target countries (assumed until December 2018). The duration of this period may vary depending on the duration of the approval and the distribution of the RMM tools in each country.

Post-implementation period: This period captures the time starting after the distribution of EM until December 2020. The start date of the period in each country will depend on the date on which the EM is approved by the respective national competent authorities.

The final dates of the study periods depend on the final schedule of the implementation of the updated RMMs in each country.

Figure 1: Overview of study periods

A single database for all target countries is not available. Therefore, a study approach was chosen which includes multiple data sources to gather drug utilisation data for oral retinoids (acitretin, alitretinoin and isotretinoin) in the European countries of interest.

Databases with longitudinal secondary patient data collected continuously over time will be used preferably to provide the most comprehensive data for the outcomes of interest.

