9.7.1 General Considerations

Given the study objectives the analyses will be mainly descriptive and will be conducted by country, by active substance and study time periods (both pre-implementation periods and post-implementation period). To allow for analysis across all data sources used in the study, a meta-analytic approach will be used to assess and pool the results from the four study countries together for each active substance (see 9.7.3.4).

The analyses will be provided for the overall class of oral retinoids and for the single active substances. Categorical variables will be presented as counts (n), proportions (%) with CI where relevant as for parameters used to address the primary objective and for the comparison of the incidence of exposed pregnancies. Continuous variables will be presented as means with standard deviation (SD) and as medians with interquartile range (IQR), where appropriate.

Changes in the reimbursement policy for contraceptives in the healthcare systems of the study countries will be considered to discard any differential misclassification of exposure.

The statistical unit will be the oral retinoid treatment episode and patient as well as prescription where appropriate. Patients who have multiple treatment episodes of oral retinoid use will be entered the cohort for analysis more than once.

The term “use” in the context of the analysis refers to the prescription or dispensing of drugs or IUD.

In the analysis, prescriptions of patients will be followed from the exposure start date to censoring date, i.e., transfer out of the database incl. death or the end of the study period, whichever comes first.

Statistical analyses will follow the tables shells validated by the MAH consortium and will be displayed using tables, listings and/or graphs. The statistical analysis will be conducted using SAS or an equivalent statistical analysis software. A detailed statistical analysis plan (SAP) will be prepared prior to data extraction.

The statistical results of all target countries and all active substances will be presented in a single report.

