It is aimed to include all patients with oral retinoid prescriptions in the analyses. However, a history of at least 3 months is necessary to cover prescriptions and laboratory pregnancy tests before treatment initiation. Analyses after treatment initiation will be performed for the following scenarios: (a) patients with a follow-up available covering the treatment episode and (b) patients with a follow-up beyond the treatment episode of at least 2 months.

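### Treatment duration gives courses still running at data end no censored status, so it is understated at least in the post-implementation period

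*Protocol*

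**What the plan says.** Section 8 lists treatment duration among the exposure characteristics to be described for the pre- and post-implementation periods. Section 9.7.3.2 fixes the end of an episode: "End of treatment duration will be defined by the date of the last prescription plus the number of days' supply of this last prescription". It then states: "The duration of treatment episodes will be provided in days". For building episodes, it leaves only the permitted gap between prescriptions to the statistical analysis plan.

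Section 9.7.1 sets the summary: "Continuous variables will be presented as means with standard deviation (SD) and as medians with interquartile range (IQR), where appropriate". It also says that prescriptions are "followed from the exposure start date to censoring date, i.e., transfer out of the database incl. death or the end of the study period". No section says how an episode that meets this censoring date enters the duration summary.

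Section 9.7.2, on the main analyses, splits the analyses after treatment initiation into two scenarios. The first is "a) patients with a follow-up available covering the treatment episode" and the second requires at least two further months. Section 9.7.3.2 does not say whether this applies to duration.

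The compared windows are both two years long. One is described as "Pre-referral: the 2-year period before referral start in July 2016" and the other runs from January 2019 to December 2020 (sections 4 and 9.1).

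**The concern.** For a course still running when observation stops, the last prescription on record is not the last prescription of the course. The end rule then writes a stop date that did not occur, and a plain mean or median treats the shortened value as a completed duration. Dropping such courses does not cure this, because a long course is more likely than a short one to be running at the cut-off, so the courses that remain are disproportionately short.

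What is at stake is the level of a stated secondary measure in at least one period and, on one reading of the follow-up rule, the comparison between periods. Section 9.9.2 acknowledges the short post-period follow-up only for the three-year acitretin measures, not for duration.

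**Working it through.** **The plan's own figure.** The protocol gives no treatment duration and no share of unfinished courses, so there is nothing to reproduce.

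**Inputs from the protocol.** Two 24-month windows (sections 4 and 9.1); an episode ends at the last recorded prescription plus supply (9.7.3.2); summary by mean and median (9.7.1). Table 5 gives 67,932 prescriptions for 20,580 Swedish patients, and 67,932 / 20,580 = 3.3 each. This is only a loose guide to course length: the patients are counted non-uniquely and a prescription need not cover 30 days.

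**Assumptions.** Starts uniform over the window, 30-day prescriptions, and the course lengths below. The protocol states none of these.

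**Fixed course length, by hand.** Take n monthly prescriptions. The k-th is seen if it falls before the cut-off, with probability 1 − (k − 1)/24. The recorded mean in months is the sum over k = 1 to n, which is n − n(n − 1)/48, so the proportional loss is (n − 1)/48.

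- n = 3: 2/48 = 4.2%
- n = 4: 3/48 = 6.3%
- n = 6: 5/48 = 10.4%
- n = 9: 8/48 = 16.7%
- n = 12: 11/48 = 22.9%

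The last prescription's supply may run past the cut-off under this rule. Cutting each course exactly at data end would give larger losses (12.5% at 6 months), but that is not the rule in 9.7.3.2.

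**Variable course length, by simulation.** 400,000 episodes per case over a 731-day window. Complete only means that episodes whose supply reaches data end are dropped, as under the first scenario of 9.7.2.

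| Model, nominal mean (days) | Truncated | Plain mean vs true | Complete-only mean vs true | Median: true / plain / Kaplan-Meier |
|---|---|---|---|---|
| Gamma, 99 | 9.4% | 93 vs 99 (−6.4%) | −4.0% | 90 / 90 / 90 |
| Gamma, 180 | 20.6% | 156 vs 180 (−13.4%) | −8.3% | 180 / 150 / 180 |
| Gamma, 365 | 45.3% | 259 vs 365 (−29.0%) | −22.2% | 330 / 240 / 330 |
| Gamma, 545 | 64.7% | 315 vs 545 (−42.2%) | −36.2% | 510 / 300 / 510 |
| Exponential, 99 | 10.0% | 91 vs 103 (−11.1%) | −14.2% | 60 / 60 / 60 |
| Exponential, 180 | 20.5% | 142 vs 182 (−22.0%) | −28.9% | 120 / 90 / 120 |
| Exponential, 365 | 39.8% | 215 vs 366 (−41.3%) | −51.9% | 240 / 180 / 240 |
| Exponential, 545 | 52.0% | 254 vs 545 (−53.4%) | −64.0% | 390 / 210 / 390 |

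(Gamma has coefficient of variation 0.5; rounding to whole prescriptions moves some true means slightly.)

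The mean is too short in every row, whether running courses are kept or dropped. At about three months the plain median is unaffected; from six months it is too low. The Kaplan-Meier median is right throughout. The Kaplan-Meier mean is limited by the 24-month window for the longest courses (497 and 403 days against 545), so for those only a median or a restricted mean is usable.

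**Effect on the pre/post comparison.** This turns on the phrase "transfer out of the database incl. death or the end of the study period, whichever comes first".

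- If the study period means each window's own end, both 24-month windows lose the same fraction for the same course lengths and start pattern. Both durations are low and the contrast is roughly balanced.
- If pre-referral courses are followed into the July 2016 to December 2018 phase, which the study also covers, they lose almost nothing. The post-period loss then appears as a fall of about 10–22% for six-month courses.

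**The case against.** Four points can be made on the other side.

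- **The post-specific effect is not established.** A reader might infer that treatment will falsely appear to shorten after the update. That needs pre-referral episodes to be followed past June 2016 for duration, and no section says so. The protocol elsewhere calls each window a study period, which favours the balanced reading. This objection stands, and the pre/post effect can only be stated conditionally.
- **Section 9.7.2 may exclude running courses.** If so, they are not recorded as finished. This also stands as a question of which rule applies. It does not remove the bias: complete-only means are 4–36% (gamma) or 14–64% (exponential) too short.
- **The analysis plan may settle it.** Section 9.7 defers detail to that plan, the permitted gap is left to it, and the mean/median rule is qualified as applying where appropriate, so a time-to-event summary could be added. That is possible, but the end-of-treatment rule is fixed in the protocol, and it produces the false stop date.
- **The size may be small.** Isotretinoin makes up 3,492/3,729 = 94% of patients in Germany, 4,546/4,842 = 94% in Spain and 20,138/20,580 = 98% in Sweden (Table 5). If courses last about three months, the loss is single-digit to low double-digit. This stands for the overall figure. The protocol nevertheless reports by substance, and a substance with long courses would be affected more.

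**Conclusion.** The concern holds in a limited form. As written, the rule understates treatment duration at least in the post-implementation period, whether running courses are closed at their last recorded supply or excluded.

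The mean recorded under the end rule is about 6–11% too short at about three months (4.2% if every course were exactly three prescriptions), 10–22% at six months, and 29–41% for variable courses averaging a year. All of these rest on assumed course lengths, 30-day prescriptions and uniform starts. They count only the cut at data end; transfer out and death would add to it. Long-term acitretin use would fall at the upper end, but the protocol gives no acitretin course length.

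The documents do not support the stronger conclusion that the study will show a false fall in duration after the update. That depends on an unstated follow-up rule for the pre-referral period. Duration is descriptive and secondary, with no test attached, so the priority is modest.

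**What to change.** In section 9.7.3.2:

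1. Treat an episode as ended only if the permitted gap after its supply end has been observed, without a new prescription, before data end, transfer out or death. Otherwise censor it.
2. Report by period and substance the Kaplan-Meier median (or a mean restricted to a stated horizon), the share of episodes censored, and the proportion still on treatment at fixed times such as 3, 6 and 12 months.
3. State one identical follow-up rule for the pre-referral and post-implementation periods, making clear what the end of the study period means in section 9.7.1.
4. State whether the follow-up scenarios in section 9.7.2 apply to duration.

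The cost is wording in the protocol, the analysis plan and the table shells, plus a standard survival procedure; no extra data are needed. The drawback is that the median may not be reached for long courses within a 24-month window. The restricted mean and the fixed-time proportions would then carry the description.

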9.3.1 Exposure Definition and Measures

Exposure will be defined as one or more prescriptions of oral retinoids (issued or dispensed) during one of the pre-defined study periods. These prescriptions will be identified using the Anatomical Therapeutic Chemical Classification System (ATC) for the target substances or the International non-proprietary name system (INN).

The exposure start date for each patient will be defined as the first prescription/dispensing record of an oral retinoids treatment episode during the pre-defined time periods. Because this study aims to assess the prescribing behaviour of HCPs, should both the prescription and the dispensing date be recorded, the prescription date would be used preferentially.

Exposure will be described by prescription length, duration of treatment and (average) daily dose and will be provided by active substance.

It will be assumed that all prescriptions and their associated dates recorded in the databases reflect actual prescription fills and subjects will start treatment at the exposure start date.

The following variables will be extracted from the data sources:

- Active substance
- Date of prescription (or dispensing)
- Pack size or days' supply
- Dosage strength
- Recommended daily dose (if available)

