9.4 Data Sources

All information on exposure and outcomes will be derived from established secondary longitudinal data sources.

Data sources are considered for the DUS based on a sufficient number of patients on oral retinoids and the availability of information relevant to describe the effectiveness of the updated PPP. Based on these criteria the following data sources will be considered (see Table 3 for more detail):

- SNIIRAM of the SNDS in France
- Collective of insurants from company health insurance funds in Germany
- SIDIAP in Spain
- National Health registers in Sweden

Table 3: Summary of various databases being considered for the DUS

Country	France	Germany	Spain	Sweden
Name and Type	SNIIRAM of the SNDS Claims database	Company Health Insurance funds Claims database	SIDIAP Sistema d'Informació per al Desenvolupament de la Investigació en Atenció Primària. Information System for Research in Primary Care	National Health registers National Drug-, Patient- and Birth registers
Overall representativeness	~88% of French population	~6% of German population	>80% of Catalanian population	National coverage for Sweden

Size	57 million, all health insurance schemes in office-based care and hospitalization	5 million insureds	About 5 million active people and about 7 million active, transferred and dead people	10 million, specialist and hospital out and in-patient care and all drugs dispensed for the Swedish population
Data available since	2009	2004	2005	2005 (1997)
Data lag time	9 months	12 months	One year	1 - 9 months (depending on the type of registry)
Patient age	Available	Available	Available	Available
Diagnosis	Available in the hospital setting; ICD-10 codes	Available; ICD-10 codes	Available ICD-10 codes	Available; ICD-10 codes
Information on physician visits	Available	Available	Available	Available
Records of laboratory pregnancy tests (for example via ICD-10 codes)	Human chorionic gonadotropin (HCG) blood tests performed	Available	Available (mainly urine pregnancy tests)	If ICD-10 code, it could be captured
Prescriptions of oral contraceptives or IUDs	Only reimbursed contraceptives	Only reimbursed contraceptives	Available	Available
Drug information for oral retinoids (date of prescription, pack size, strength)	Available; duration approximated algorithmically	Available; duration approximated algorithmically	Available	Available; duration approximated algorithmically
Pregnancy	Available	Available	Available	Available

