All medicines are prescribed electronically in Sweden. The National Prescription Register tracks the full details of all dispensed medications at individual patient-level in Sweden since July 1, 2005. Patients are followed longitudinally through their personal identification number, regardless of which pharmacy they visit. The National Drug Register is updated monthly and covers all sales from Swedish pharmacies.

The available data in the National Drug Register include:

- Patient demographics (age, gender, and residency)
- Prescription information (date of prescription, prescriber's specialty, WHO ATC code, and brand name)
- Dispatch information (dispatch date, product number, total dose dispatched, number of packages dispatched, and drug cost)
- Product information (Package size, formulation, etc.)

Information on prescribed dose is only documented in free text format where available, and days' supply is not recorded.

In Sweden, the online database on prescription held by the National Board of Health and Welfare provides the following information on the annual prevalence of Swedish women aged 15-49 years who filled at least one prescription for hormonal contraceptives in 2012-2017: ATC G02B contraceptives for topical use: 4.3-5.4%; ATC G03A hormonal contraceptives for systemic use: 22.4-26.1% (reference: prescription registry).

Of note, to gain access to the linked register an approval from the local ethical review board is necessary, whereby the research project and ethical aspects should be explained in a formal application. The ethics approval is dependent on the data being made publicly available in some form. Please see below for more detailed information on the information contained in each register.

The Medical Birth Register contains information on 97% to 99.4% of all pregnancies resulting in delivery in Sweden and is frequently used for quality work and for research (National Board of Health and Welfare, Sweden 2012; Olausson PO, 2002). The register contains detailed information about mothers and new-borns. However, pregnancies are only captured after 22 weeks. The identification and timing of pregnancies will be done according to published methodology (Stephansson et al. 2018).

Records on pregnancies are also documented in the National Patient Register regardless of the duration of pregnancy, but missing information regarding early termination needs to be taken into account.

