9.7.6 Handling of Missing Data

Due to the nature of real-world data, some data points might be missing from the databases for a number of reasons. The number and type of missing values will be recorded and reported in the final study report. Statistical calculations (i.e. the denominator) will be adjusted accordingly for the analysis.

Information on recommended daily dose may be not available from all data sources. The proportion of missing values will be described. However, the degree of completeness varies between databases. The missing information will be highlighted. In case dose recommendation is missing, dose information from the SPC will be used.

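### Where days' supply is filled in from the label dose, average daily dose partly or wholly returns that assumed dose, so a before-after change in dosing is hidden or attenuated

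*Protocol*

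**What the plan says.** Dose is one of the exposure characteristics to be described before and after implementation (Protocol section 8, secondary objectives). Section 9.7.3.2 defines it: "The average daily dose will be analysed over a treatment episode based on dosage strength, pack size or day supply and number of prescriptions per" (the unit being the episode). No denominator is named.

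The same section sets a three-step order for prescription length. It uses the "days' supply reported with this prescription or, when not available, pack size and the recommended daily dose by the physician (if available"), and failing that the length is set "by default, according to the information of strength connected with the prescription and SmPC". Section 9.7.6 repeats the last step for dose: "In case dose recommendation is missing, dose information from the SPC will be used".

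On what is recorded:
- **All sources:** section 9.3.1 extracts a recommended daily dose only if available.
- **Sweden (9.4.3.1):** "Information on prescribed dose is only documented in free text format where available, and days' supply is not recorded".
- **France, Germany and Sweden (Table 3, section 9.4):** the drug-information cell reads "Available; duration approximated algorithmically".
- **Germany (9.4.1.2):** the prescription fields listed are product code, cost and date.
- **France (9.4.1.1):** no prescribed dose is listed.

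Section 9.7.3.2 also defines episode length: "End of treatment duration will be defined by the date of the last prescription plus the number of days' supply of this last prescription". The start is the first prescription date.

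**The concern.** A dose estimate needs a quantity and a time over which it was taken. The fallback rule obtains the time by dividing the quantity by an assumed dose. Dividing the quantity by that time gives the assumption back. To the extent this happens, the tables for the two periods show similar doses because the same assumption was entered twice, and a reader would take that as unchanged dosing. How far it happens depends on the denominator and on how often the fallback is reached. The protocol fixes neither.

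**Working it through.** The protocol states no figure for average daily dose, so there is none to reproduce. The check is algebraic.

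**Set-up.** Let k be prescriptions per episode, M the milligrams per prescription (taken as equal), d the dose actually taken and a the dose assumed from the label. Doses are in relative units. Each refill is assumed to occur when the previous pack runs out, so the observed interval is M/d and the imputed supply is M/a.

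**Reading A: denominator is summed imputed supply.** Average dose = kM / (kM/a) = a, for any d and any k. A true change of any size shows as 0%.

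**Reading B: denominator is the episode duration of section 9.7.3.2.** Duration = (k−1)M/d + M/a, so average dose = k / [(k−1)/d + 1/a]. At k = 1 this is again a.

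**Value of k.** The only prescriptions-per-patient ratio for a retinoid that Table 5 supports is Swedish. For isotretinoin it is 66,225 / 20,138 = 3.29. The table footnote calls these patients non-unique, and the ratio is per patient, not per episode, so a range of k is shown.

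**Change shown under reading B, with a = 1 and starting dose 1.0:**

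| k | true +20% shows as | true −20% shows as |
|---|---|---|
| 1 | 0% | 0% |
| 2 | +9.1% | −11.1% |
| 3 | +12.5% | −14.3% |
| 3.29 | +13.1% | −14.8% |
| 6 | +16.1% | −17.2% |

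Worked line at k = 3.29: 3.29 / (2.29/1.2 + 1) = 1.131. So 13.1/20 = 66% of the rise is visible, and 14.8/20 = 74% of the fall.

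**Level under reading B.** With true dose 1.0 and k = 3.29, the estimate is 0.91 if a = 0.75 and 1.11 if a = 1.5. It is pulled toward the assumed dose.

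**Dependence on k.** Hold the true dose at 1.0 with a = 0.75 (an illustration). At k = 3 the estimate is 3 / (2 + 1.333) = 0.900. At k = 6 it is 6 / (5 + 1.333) = 0.947. The ratio is 1.05: an apparent 5% rise with no change in dose. Prescription interval is itself a primary outcome (section 9.7.2), so k may differ between periods.

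**Splitting of episodes.** If the true dose is half the assumed dose, a supply counted as 30 days lasts 60, which leaves an apparent gap of 30 days. Depending on the allowed gap, which is left to the SAP, such an episode may break into single-prescription episodes, where the result is a.

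**The case against.** The strongest reply is that the dose sentence speaks of analysis over a treatment episode, and the same section bounds the episode by recorded dates plus the last supply only. On that reading most of the time is observed and a change remains visible. This stands, and it rules out saying that the measure cannot show a before-after change. It does not clear the measure: reading B still shrinks changes, varies with k and returns the assumption at k = 1.

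Second, the label is the last of three steps, and algorithmic approximation of duration is not the same as use of the label dose. Sweden has some free-text dose. This also stands. A reader might infer from Table 3 that all patients in three of the four countries are affected, but the protocol gives no fallback share for any country.

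Third, the default also uses strength, so the assumed dose need not be one constant. That is correct, but a shift in strength mix passing through the rule would still not be a measurement of daily intake.

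Fourth, section 9.7.6 promises to describe the proportion of missing values. That discloses the extent of the problem but leaves the imputed values in the outcome.

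Fifth, dose is a secondary, descriptive item with no planned test, and analysis detail belongs in the SAP, which is not shown. The limited consequence is conceded. The point is not an absent detail, though: the SmPC imputation is stated in the protocol and enters the reported dose under either reading.

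**Conclusion.** The point holds in a limited form. Wherever supply is label-imputed, average daily dose equals the assumed dose in single-prescription episodes, and in all episodes if summed supply is the denominator. With episode duration as denominator it is pulled toward the assumed dose. A true 20% rise then shows as about 13%, and a 20% fall as about 15%, at 3.29 prescriptions. For k from 2 to 6 the rise shows as 9% to 16%. These figures assume equal packs, refill at run-out, and that the Swedish per-patient ratio is a fair guide to prescriptions per episode.

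The number of prescriptions affected is unknown. Sweden is the clearest case because days' supply is absent and dose is free text at best. France and Germany are likely but cannot be quantified from the protocol. The documents do not support reading the plan as fully circular, or as affecting every patient in those three countries. Nor do they establish that daily doses are recorded in Spain: the Table 3 row concerns date, pack size and strength. The primary prescription-interval outcome rests on prescription dates and is not affected by this calculation.

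**What to change.** In section 9.7.3.2, for episodes with label-imputed supply and at least two prescription dates, define average daily dose as the milligrams supplied before the last prescription divided by the days from first to last prescription date. Combine strengths prescribed on the same day. Under the assumptions above this gives (k−1)M / [(k−1)M/d] = d, with no label dose in the calculation.

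Report single-prescription episodes with imputed supply as dose not estimable. In section 9.7.6, exclude SmPC-imputed values from the dose outcome, and show the label-imputed share by country and period.

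The cost is wording and a different formula. Date, strength and pack size are already extracted (section 9.3.1). There are two drawbacks: dose will be described only in multi-prescription episodes, which are a selected group, and late refills bias the estimate downward. Imputed supply may still influence which prescriptions are joined into an episode through the gap rule, so that rule should be read together with this change.
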